## Significance

Greater than two million Americans are estimated to currently suffer from opioid use disorder (OUD), and over the past two decades, opioid related mortality has exponentially increased. Buprenorphine is a Food and Drug Administration (FDA) approved treatment for OUD management. Reflective of its long-term, life-saving benefits, buprenorphine is currently the most frequently prescribed medication in the state of Maine, with the blood pressure medication, hydralazine, being the second most commonly prescribed. Buprenorphine works by binding strongly to opioid receptors- targets for drugs of abuse - for relatively extended periods of time, attenuating the cravings and withdrawal symptoms that fuel opioid addiction and relapse. When individuals on buprenorphine present for surgery, their acute post-surgical pain can be challenging, as the opioid medications commonly given to provide analgesia are unable to easily displace buprenorphine. Currently, both buprenorphine discontinuation and continuation are recognized as acceptable standards of care. The Substance Abuse and Mental Health Services Administration (SAMHSA), the organization that manages the federal approval of buprenorphine prescribers, recommends either perioperative buprenorphine continuation or discontinuation, based upon patient and provider preference, with consideration of the inherent risks for each management strategy. However, there is limited specific guidance on the optimal perioperative management of buprenorphine in this patient population and low dose buprenorphine continuation is not currently described as a treatment option by SAMHSA .

Preliminary clinical observations support that buprenorphine continuation at low analgesic doses can adequately facilitate postoperative pain management without interrupting OUD treatment. However, no prospective trial has investigated this treatment strategy. The purpose of this study is to investigate whether buprenorphine continuation at analgesic dosing is superior to buprenorphine continuation in individuals presenting for elective surgery. Adults scheduled for

elective surgery who are taking  $\geq 12$ mg buprenorphine for OUD treatment will be eligible for this study. Enrolled participants will be randomized to receive either a reduced analgesic dose of buprenorphine (8mg) or to continue buprenorphine on the day of surgery without dose reduction. Our primary outcome of interest is postoperative pain scores. Our secondary outcomes of interest are opioid consumption, opioid dispensing up to 30 days following the surgical procedure and OUD related symptoms, including opioid withdrawal, cravings and relapse. We hypothesize there will be a clinically significant increase in pain scores when buprenorphine is continued in full compared to when it is continued at a lower analgesic dose. We will define clinical significance as a difference in composite pain scores of greater than 20% between groups. We also hypothesize that opioid consumption and opioid dispensing will be greater with full dose buprenorphine continuation compared to low-dose continuation. This will be the first randomized trial comparing competing perioperative buprenorphine treatment strategies and will yield critical preliminary data for larger, confirmatory studies. Additionally, we envision that this study will lay groundwork for follow-up investigations in this patient population, focused on preventing opioid cravings and relapse perioperatively, along with other clinical scenarios where acute pain is anticipated, such as intensive care unit settings.

Successful execution of this prospective trial will provide [name] with the tools and critical experience necessary to pursue her aspirations of becoming a successful clinical investigator. [name] has a mentorship team that is committed to her success and is led by her department chair, [name]. Her mentorship team also includes [name], [name], [name], [name], [name] and [name]. Her mentorship team will help provide guidance as she mentors residents, including [name], that have expressed interest in engaging in clinical research. They will meet with her periodically and provide her with any feedback that is required, based upon the trial phase, to help promote successful trial completion.

## **STUDY DESIGN AND RESEARCH PROCEDURES**

This is a prospective, randomized, unblinded clinical trial comparing full dose buprenorphine continuation to buprenorphine continuation at analgesic dosing in adults with OUD maintained on 12mg or greater sublingual equivalent buprenorphine, who are scheduled for elective surgery.

### ***Randomization Plan***

Enrolled participants will be randomized 1:1 into one of two groups (defined below). The randomization scheme will be developed using NQuery Software (Statistical Solutions, Boston, MA).and will use permuted blocks of 4 and 6 patients to ensure balance between study arms. The analyst will provide the research coordinator with randomization assignments in sequentially-numbered opaque envelopes (one series of envelopes for each stratum of anticipated post-surgical pain) . The study coordinator will pass the next envelope in sequence to another member of the study team when it is time to assign a subject to a group. Gerbershagen et. al. documented the distribution of pain scores for 179 different surgical procedures and we will use these data to establish randomization strata. For true practice generalizability on the association between buprenorphine management and postsurgical pain control, we will include surgical procedures based on average pain intensity on postoperative day (POD) 1, as opposed to limiting our criteria to a particular surgical type (see Appendix 1).

Patients will be stratified according to their anticipated pain score on POD 1 (4-6/10 range vs >6/10 range) and those within each stratum will be randomized to one of two groups as follows:

- FULL-BUP group: buprenorphine formulation continued throughout the perioperative period
- STD-BUP group: buprenorphine formulation reduced to 16mg the day prior to surgery and then 8mg on the day of surgery onwards. Participants in this group taking 12-16mg buprenorphine at baseline will have no change to their buprenorphine dose on the day prior to surgery.

All participants will be transitioned back to their regular dose of buprenorphine when postoperative surgical pain has subsided as determined by their

buprenorphine provider following hospital discharge. This transition will be coordinated with their buprenorphine provider, which is our current standard practice when buprenorphine is reduced perioperatively.

As the study is unblinded, both patients and providers will be aware of the randomization assignment. To help mitigate bias, the team members collecting and entering data will be masked regarding the patient's assignment. The REDCap database has the randomization assignments in an instrument separate from the study data collection instruments, allowing for data entry without seeing which group the subject is in.

### ***Study Procedures***

On the day of surgery, prior to the procedure, participants will be asked to complete a series of questionnaires to obtain baseline self-assessments for opioid cravings, opioid misuse, and opioid withdrawal symptoms (see protocol schema and Measures for Aim 3 section for details). Patients will be asked to report early for their procedure to complete the study questionnaires in a private space.

Both groups will receive identical preoperative, intraoperative and postoperative multimodal opioid sparing strategies, coordinated with the surgical, anesthetic, and psychiatric clinical care teams directly involved in the study participant's care. Multimodal analgesia, or the administration of two or more drugs that act by different mechanisms, provides more effective analgesia compared to medications used individually. Multimodal analgesia has been well established at achieving early recovery after surgery and reducing pain scores. According to the American Society of Anesthesiologists (ASA) task force for acute pain management, multimodal pain management therapies should be used for the treatment of surgical pain whenever possible however it is not mandatory to use these methods routinely for all surgical procedures and they are utilized at the discretion of the anesthesiologist taking care of the patient. As such, we will adopt this standard of care practice for the treatment of post-surgical pain in both randomized groups. Our multimodal analgesic strategy will consist of gabapentin, acetaminophen and Celebrex preoperatively and postoperative ketorolac, acetaminophen, opioids, nerve blocks infusions/epidural catheters, alpha agonists,

ketamine and lidocaine infusions as indicated. Postoperatively, opioid medications will be given IV or PO as second line analgesic agents. If a participant has an allergy or aversion to any of these medications, they will not receive the medication, but will be able to participate in the study with alternative medications. All analgesic medication administered will be documented by study staff. In the event of poorly controlled pain at any point during the study, we will provide the patient with appropriate analgesic rescue agents to ensure that post-surgical pain is adequately controlled.

Intraoperative opioid consumption, type of anesthesia, total PACU opioid consumption, normalized for time spent in PACU, and 24, 48 up to 72-hour opioid consumption will be extracted from the patients' charts. All opioid consumption will be converted into MME. One month postoperatively, participants will receive virtually- administered questionnaires, including: a substance use evaluation, where they will be asked to complete self-assessments identical to those administered on the day of surgery for comparison analysis. Patients will be encouraged to record postoperative pain and opioid consumption on the Timeline website regularly and reminded that compensation is tied to completion. Reminder phone calls will be made by study staff during this time period.

We will contact each participant's buprenorphine provider to collect data for buprenorphine treatment retention following surgery and will assess each patient's Maine Prescription Awareness Tool (MainePAT) record to collect data for outpatient opioid utilization during the 30 days following surgery. Buprenorphine formulations will not be included in our MME total.

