#### Measures for Aim 1 (Pain scores)

The primary outcome of this study will be composite pain scores 24 hours after surgery. Others have shown that composite pain scores quantify pain with greater accuracy than a single measurement. Jensen et. al. concluded in their study that composite pain intensity scores from two or more individual ratings of pain are valid for detecting treatment effects. Pain scores will be measured using a numeric rating scale (NRS) (0=no pain; 10= worst possible pain). "Worst," "average," and

“least” pain scores will be assessed for the preceding time interval at 24, 48, and 72 hours following surgery. Inpatient pain scores will be collected as part of routine post-operative care and will be extracted from the medical record; there is no set protocol for routine pain score collection but typically it is done every 4-8 hours. To collect pain scores, nursing staff asks patients to rate their current pain on a scale from 0-10. If a participant is discharged prior to 72 hours after surgery, NRS scores will be assessed at the remaining time points via telephone. Prior to discharge, study staff will provide patients with a log to keep a record of their pain scores, at least once every 8 hours, in order to mitigate recall bias in anticipation of being contacted by research staff. Study staff will call discharged patients and ask them to report their pain scores for each 24 hour period between discharge and 72 hours postoperatively as recorded on the forms they were given at time of discharge.

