***Source of subjects, recruitment and retention methods:***

Participants will be recruited when they attend their pre-surgery appointment at the MMC Pre-Operative Readiness Education Program (PREP) clinic. Currently, the majority of patients scheduled for surgery receive consultation from the PREP Clinic, within two months prior to their procedure. Patients who are potentially eligible for the study will be identified by the PREP nurse practitioner or the physician provider who conducts the preoperative evaluation. As part of an IRB reviewed quality improvement project (IRBNet #15892224-1) there is a dashboard in Epic that identifies patients scheduled for surgery who are on buprenorphine. Study staff will review this dashboard to identify potential candidates for this study. The standard practice at MMC is when a patient is identified taking buprenorphine/naloxone through the preoperative chart review, the patient is referred to an anesthesiologist for instructions on the management of buprenorphine/naloxone prior to surgery. Our recruitment method for study participants, therefore, does not differ from this current established practice. A member of study staff will then contact patients by calling the number obtained from the Epic Dashboard. We will introduce the study, and any patient who is interested in learning more about the study and potentially participating will have a consent form sent to them. The informed consent form will be provided electronically, or by mail, for the patient to review. If patient requests the consent be mailed, a follow up phone call will be scheduled. During this phone call, further questions will be answered. Because consent needs to be given prior to day of surgery in order to randomize patients for this trial, we will use DocuSign to obtain consent electronically for patients who would like to participate in the trial.

Patients who choose to participate in the study will receive a phone call within one week prior to their surgery to confirm the buprenorphine management plan that they were assigned (see randomization plan, above). Participant confidentiality will be maintained throughout the consent process.

Participants will be reminded that their involvement in the study is completely voluntary and that they can choose to withdraw from the study at any point. They will also be advised that withdrawing from the study would not affect the care they

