### ***Biostatistical Analysis***

#### **Sample Size:**

We estimated study size based on postoperative pain scores in a recent study of surgical patients at our institution (manuscript submitted); mean NRS was  $50 \pm 28$ . Our estimate for effect size is based on published data showing that a difference in NRS of 20/100 points is clinically significant. A sample size of 32 per group will have 80% power to detect a difference in means of 20 (the difference between a Group 1 mean,  $m_1$ , of 50 and a Group 2 mean,  $m_2$ , of 30) assuming the common standard deviation is 28 using a two group t-test with a 0.05 significance level. To account for dropout, we will enroll an additional 8 patients for each group for a total sample size of 80 patients.

Statistical Analysis:

Data will be summarized using descriptive statistics and will be presented as means (SD), medians [IQR] or frequency counts (%), as appropriate. Data will be analyzed on an intention to treat basis. We will first examine the success of randomization by comparing covariates demographic and clinical covariate measurements between the FULL-BUP and STD-BUP groups; to conserve study power, no formal statistical comparison will be performed and the data will be reviewed visually. Next we will perform univariate analyses to compare outcome measures between the FULL-BUP and STD-BUP groups, using a two-sided t-test or Mann Whitney U test for continuous variables and chi square or Fisher exact tests for categorical data, as appropriate. For paired analysis of pre/post surgery instruments, we will use McNemar's test or the Wilcoxon test, as appropriate. We will then explore the relationships between demographic and clinical variables and outcome measures in bivariate analyses, using the above methods or Pearson's and/or Spearman's correlation, ANOVA or Kruskal-Wallis test, as appropriate. Finally, we will explore further any observed differences in outcome measures between study arms by adjusting for covariates using analysis of covariance or (in the event of missing data), mixed models regression. Covariates will be entered into the model if they demonstrate a significant ( $p \leq 0.1$ ) association with outcome measures in bivariate analyses.

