We will perform an interim analysis at 50% enrollment and will terminate the study if a significant pain score difference is detected. Significance for the interim analysis will be accepted at  $p < 0.003$ , based on 2 sequential tests and using an O'Brien-Fleming spending function to determine test boundaries. Significance overall will be accepted at  $p < 0.047$  to account for interim analysis. All statistical analyses will be performed by the Navigation team at CORE using SPSS Statistical Software version 27 (IBM SPSS Inc., Armonk, NY).

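### No preoperative pain score is listed for a 24-hour pain endpoint; one taken before randomisation and used in a prespecified ANCOVA would add precision, by an amount that depends on a correlation the documents do not give

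*Combined protocol and SAP*

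**What the plan says.** - **Endpoint.** Measures for Aim 1 makes the composite NRS at 24 hours primary. Worst, average and least "pain scores will be assessed for the preceding time interval at 24, 48, and 72 hours following surgery". No earlier pain rating is scheduled.
- **Preoperative data.** Study Procedures has patients complete questionnaires on the day of surgery "to obtain baseline self-assessments for opioid cravings, opioid misuse, and opioid withdrawal symptoms". Specific Aims and Measures for Aim 3 name the PHQ-9, DDQ, OCS, COMM, Timeline Follow-Back and COWS. None is listed as a pain score.
- **Stratification.** The Randomization Plan stratifies on the pain expected on POD 1 from the procedure (4-6 versus above 6), not on the patient's own pain. Subject Selection does not exclude patients with existing or chronic pain.
- **Analysis.** Statistical Analysis compares the arms "using a two-sided t-test or Mann Whitney U test for continuous variables". Covariate adjustment is a later exploratory step, applied where differences are observed, with covariates admitted at p ≤ 0.1. No covariate is named.
- **Contacts before surgery.** In the recruitment section, "A member of study staff will then contact patients by calling the number obtained from the Epic Dashboard" to introduce the study. Consent is signed by DocuSign, and a follow-up call is tied to requests for a mailed form. The call in the week before surgery confirms the plan already assigned, so it comes after randomisation.

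**The concern.** Appendix 1 includes joint replacement, spinal fusion, laminectomy and amputation alongside hernia repair and thyroidectomy. Two patients in the same stratum may come to surgery with very different pain, and that difference may still show in the 24-hour score. As listed, the plan would hold no record of it. It could not appear in the visual baseline review, and no later model could use it.

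Two things are at stake. The first is precision: any part of the SD of 28 that existing pain explains stays in the error term. The second is interpretation: with about 32 evaluable patients per arm, an accidental difference in existing pain is quite possible, and a reader of the results could neither see it nor allow for it.

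**Working it through.** **Inputs from Sample Size.** "A sample size of 32 per group will have 80% power to detect a difference in means of 20", "assuming the common standard deviation is 28", "using a two group t-test with a 0.05 significance level". Eight more per arm are enrolled for dropout, giving 40 per arm. The final-analysis threshold is 0.047 because of the interim look. The correlation r between a preoperative NRS and the 24-hour composite is not given, so a range is shown.

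**Step 1: the plan's own figure.** The standard error is 28 × √(2/32) = 28 × 0.25 = 7.0. The noncentrality is 20/7.0 = 2.857 on 62 degrees of freedom. The two-sided t-test at 0.05 then has power 80.3% with 32 per arm and 79.0% with 31. The stated 32 is reproduced.

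**Step 2: power with the covariate.** Residual SD = 28 × √(1 − r²), noncentrality = 20/(residual SD × 0.25), one degree of freedom fewer.

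| r (assumed) | Residual SD | Noncentrality | Power, 32 per arm | Gain over 80.3% (points) |
|---|---|---|---|---|
| 0 | 28.0 | 2.857 | 80.3% | 0.0 |
| 0.2 | 27.4 | 2.916 | 81.9% | +1.5 |
| 0.3 | 26.7 | 2.995 | 83.8% | +3.5 |
| 0.4 | 25.7 | 3.117 | 86.6% | +6.3 |
| 0.5 | 24.2 | 3.299 | 90.1% | +9.8 |
| 0.6 | 22.4 | 3.571 | 94.0% | +13.7 |

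The equivalent sample-size factor is 1/(1 − r²): 1.04, 1.10, 1.19 and 1.33 for r = 0.2, 0.3, 0.4 and 0.5.

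**Step 3: sensitivity.**
- Threshold 0.047, 32 per arm: the base is 79.5%, and the gain is +3.6 points at r = 0.3 and +10.1 at r = 0.5.
- All 40 per arm analysed, threshold 0.05: the base is 88.4%, and the gain is +2.7 points at r = 0.3 and +7.0 at r = 0.5.
- Allowing for the average chance imbalance in the covariate (residual SD multiplied by √(1 + 1/60), where 60 = 2 × 32 − 4): power is 79.6% at r = 0, 83.2% at r = 0.3 and 89.6% at r = 0.5. The worst case is therefore a loss of about 0.7 points.
- The stratum as a second covariate takes one more degree of freedom. At 32 per arm this lowers the powers in the table by about 0.02 points, before counting any variance that the stratum explains.

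**Step 4: chance imbalance.** In units of its own SD, the between-arm difference in preoperative pain has standard error √(2/32) = 0.25. At r = 0.4, an imbalance of one standard error moves the unadjusted difference by 0.4 × 0.25 × 28 = 2.8 points on the 0-100 scale. An imbalance of two standard errors moves it by 5.6 points, against a target of 20. This movement is already part of the standard error of 7.0; it is not added to it.

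**Step 5: timing.** The day-of-surgery session follows randomisation in an unblinded trial. By then, STD-BUP patients above 16 mg at baseline have had a dose change the day before. A pain score taken there could be affected by the allocation and would not be a clean baseline covariate.

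**The case against.** **The plan is valid without this score, and that stands.** Randomisation balances existing pain in expectation, and the standard error already allows for chance imbalance. A reader might infer that the primary comparison is biased, or that a preoperative score would separate existing pain from surgical pain. The documents support neither inference. A covariate improves precision and corrects for chance imbalance; it does not divide the 24-hour score into parts.

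**The size of the gain is unknown, and that stands.** A gain of 4 to 10 points is tempting to state as fact, but it needs r between 0.3 and 0.5 and a changed primary analysis. At r = 0.2 it is 1.5 points.

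**Stratification does part of the work.** Knee and shoulder replacement and spinal fusion are in the severe stratum, and hernia repair is in the moderate one. The cover is incomplete, because hip replacement, laminectomy and amputation are also in the moderate stratum. If the stratum explains some of the variance, the further gain is smaller than the table shows.

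**Collection is not entirely free.** No call is guaranteed between consent and randomisation. The preoperative clinic visit can be up to two months before surgery, so a score taken around then may be weeks old and correlate less well with the endpoint.

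**Absence is shown only for the text available.** Study Procedures refers to a protocol schema for details. That figure, and some text between Biostatistical Analysis and Limitations, could not be seen. Statistical Analysis also mentions clinical covariates without listing them.

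Finally, the plan reaches 80% power on its own assumptions, and Significance presents the trial as yielding preliminary data for confirmatory studies. This is a reason for proportion, not for leaving the score out: it must be collected before randomisation or not at all.

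**Conclusion.** The point holds as one of precision and transparency. In the text available, the primary pain outcome has no preoperative counterpart, so existing pain can be neither shown by arm nor adjusted for.

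A pre-randomisation score in a prespecified primary ANCOVA would raise power from 80.3% to between 81.9% and 90.1% for correlations of 0.2 to 0.5, with 32 per arm. If all 40 per arm are analysed, the gain is 2.7 to 7.0 points for correlations of 0.3 to 0.5. If the correlation is zero, the loss is under one point. The figures rest on the plan's SD of 28 and difference of 20, a linear relation between the two scores, and a correlation that is assumed. They come from the change of analysis: collecting the score and keeping the unadjusted test gains nothing.

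The change is worth making because it costs little, not because the present plan is invalid.

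**What to change.** 1. After consent and before the envelope is opened, record average pain over the past week on the 0-10 NRS. It can be an item sent with the electronic consent form or one question by phone, taken as close to surgery as the randomisation schedule allows.
2. Record the date of the score and show the score by arm in the baseline table.
3. Make the primary 24-hour comparison an ANCOVA with this score and the randomisation stratum as fixed, prespecified covariates. This replaces the unadjusted test followed by p ≤ 0.1 screening for that outcome. Use the same model at the interim look, and state how missing baseline scores will be handled.
4. Do not use a day-of-surgery score as the covariate.
5. If the schema or another part of the protocol already provides a preoperative pain score, name it, confirm that it precedes randomisation, and go to step 3.

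Cost: one item, one REDCap field, a rewritten primary-analysis paragraph, possibly a brief extra contact for some patients, and a few missing baseline values. The sample size need not change.

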#### ***Subject Selection***

Inclusion Criteria: Male or female; aged 18-75 years; American Society of Anesthesia (ASA) health class I-III; currently taking buprenorphine formulations equivalent to 12mg or greater for at least the prior 30 days for treatment of OUD (as defined by the Diagnostic and Statistical Manual of Mental Disorders- 5 (DSM-V) criteria); scheduled for surgery at MMC or SSC where a procedure with a greater than 4/10 intensity is expected on POD 1 (see Gerbershagen et.al. and appendix 1 for list of surgeries).

Exclusion Criteria: Unable to consent to the study; currently pregnant; current major medical illness that could limit the ability to utilize medications within our protocol driven multimodal analgesic plan (e.g. cancer, severe end-stage organ disease, or dementia).

Inclusion of women and minorities. We will not exclude any adults on the basis of age, gender or ethnicity and our projected enrollment is based on most recent Maine census. See appendix 2 for projected enrollment table.

Inclusion of individuals across the lifespan. We will exclude individuals under the age of 18 years from enrollment in this trial. These patients require personalized treatment strategies often coordinated by multiple providers therefore we will not alter these treatments decisions for study purposes.

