### **Safety**

We will ensure that appropriate plans are in place to guarantee the safety of enrolled subjects. All patients will be made aware of the possible risks associated with treatment group to which they are randomly assigned, as well as the risks inherent in experiencing postoperative pain. For instance, both groups are at risk of experiencing OUD symptom exacerbation. The use of opioid agonists and perioperative pain itself may be risks for OUD symptom exacerbation and relapse. Reduction of buprenorphine to 8 mg before surgery as well as full dose buprenorphine continuation can potentially lead to OUD relapse since exposing patients to opioids with similar properties to the agents they abused in the past as management of their acute post-surgical pain can serve as a trigger for relapse. However, this risk is inherent in the current MMC standard of care.

Another potential risk is difficult post-operative pain control due to buprenorphine continuation since the pharmacokinetics of buprenorphine may interfere with the effectiveness of full opioid agonists used for pain control. However, this risk is not greater than the current risk to patients, since full dose buprenorphine continuation is a practice endorsed by SAMHSA. If patients experience poorly controlled pain, they will receive opioid and non-opioid rescue analgesic agents such as nerve blocks or epidurals when indicated, ketamine infusions, and alpha agonist medications, as determined necessary by the treatment providers caring for the

patient. All participants will be transitioned back to their regular dose of buprenorphine when postoperative surgical pain has subsided as determined by their buprenorphine provider following hospital discharge. This transition will be coordinated with their buprenorphine provider, which is our current standard practice when buprenorphine is discontinued, or the dose is reduced, perioperatively.

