### ***Limitations***

[figure not shown]
A study limitation is that pain scores, craving scales, and drug use are all self-reported measures, therefore complete accuracy cannot be assured. However, our randomization design should help prevent the introduction of bias, as inaccuracies based on self-report subjectivity would be randomly distributed between the two treatment arms. To encourage accurate drug-use reporting, we will remind participants that information they provide regarding drug use will not be included in their patient record, nor will their providers have access to the information. Another limitation is that our study does not have a placebo arm, however, since randomization occurs prior to hospital admission and physical interaction with study staff, it is impractical to provide patients with placebo medication at the time of study commencement. An additional limitation is that the study is not blinded to patients or treatment providers, however, we attempt to mitigate this limitation by masking the data collection and data entry, as described in the study design and research procedures section.

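### The p ≤ 0.1 covariate screen is not limited to variables fixed before allocation, so the exploratory adjusted model could adjust for anesthetic or analgesic technique given after it

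*Combined protocol and SAP*

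**What the plan says.** All references are to the combined protocol and SAP.

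- **Study Procedures** says that "Both groups will receive identical preoperative, intraoperative and postoperative multimodal opioid sparing strategies". It then says of multimodal methods that "they are utilized at the discretion of the anesthesiologist taking care of the patient", and adopts that practice in both arms. Blocks, epidurals, alpha agonists and infusions are given when indicated. Study staff document every analgesic given, and type of anesthesia and intraoperative opioid use are taken from the chart.
- **Safety** lists, for poorly controlled pain, "rescue analgesic agents such as nerve blocks or epidurals when indicated, ketamine infusions, and alpha agonist medications".
- **Randomization Plan** says that "both patients and providers will be aware of the randomization assignment". **Limitations** places allocation ahead of treatment: "since randomization occurs prior to hospital admission and physical interaction with study staff".
- **Biostatistical Analysis** compares the arms unadjusted first, by intention to treat. It next relates demographic and clinical variables to the outcomes. It then explores any arm differences seen by adjusting for covariates, entering those associated with outcome at p ≤ 0.1. No list of covariates is given, and nothing says that they must precede allocation.

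**The concern.** A covariate measured before allocation cannot be affected by the arm, so adjusting for it leaves the meaning of the arm difference intact. A technique chosen after an open allocation has no such protection. Two routes matter.

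- **The technique responds to pain.** If one arm has more pain, it receives more blocks or ketamine. Technique use then partly stands in for the outcome, and holding it fixed removes part of the arm effect.
- **The technique responds to the arm.** If clinicians add techniques because of the assignment, that use is part of what the arm does under a strategy comparison. Holding it fixed takes that part out again.

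A screen on association with outcome is likely to pick such variables, because analgesic techniques are given to change pain. A reader of the adjusted estimate could not tell which route had operated, and the two move the estimate in opposite directions.

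**Working it through.** **1. The plan's own figure.** Inputs from Biostatistical Analysis: difference 20, SD 28, 32 per arm, two-sided t-test. Noncentrality = (20/28) × √(32/2) = 2.857 on 62 degrees of freedom. Power is 80.3% at alpha 0.05, which reproduces the stated 80%, and 79.5% at the final alpha of 0.047.

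**2. Simulation inputs.** From the plan: 32 per arm, SD 28, means 50 and 30 (taken here as FULL-BUP 50, STD-BUP 30, the hypothesized direction), alpha 0.047, entry at p ≤ 0.1. Assumed, because the documents give no technique effect or usage rate: the technique lowers the score by 10, 20 or 30 points, with use as described below. There were 20,000 trials per setting. The technique enters the ANCOVA if a t-test of pain by technique gives p ≤ 0.1. Results are for trials where it enters.

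**3. Rescue-only use (12 settings).** The technique is given if the underlying score plus noise (SD 15 or 25) exceeds 60 or 70.

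Hand check for trigger 60, noise 15, effect 10:
- SD of the triggering score = √(28² + 15²) = 31.8.
- Use in FULL-BUP = 1 − Φ(10/31.8) = 37.6%; in STD-BUP = 1 − Φ(30/31.8) = 17.2%.
- Expected unadjusted difference = 20 − 10 × (0.376 − 0.172) = 18.0, as simulated.

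| Setting | Unadjusted | Adjusted | Rejection at 0.047 |
|---|---|---|---|
| Trigger 60, noise 15, effect 10 | 18.0 | 11.6 | 79% to 53% |
| Trigger 70, noise 25, effect 30 | 16.6 | 14.4 | 77% to 63% |
| Range over 12 settings | 14.4 to 18.6 | 11.5 to 14.5 | 72–79% to 53–64% |

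The drop is largest in the first row (1 − 11.6/18.0 = 36% from rounded figures, 35% unrounded) and smallest in the second (13% rounded, 14% unrounded). The technique enters in 30% to 100% of trials.

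**4. Arm-driven use (6 settings).** Use is 30% in STD-BUP and 40% or 50% in FULL-BUP, unrelated to pain. For 50% versus 30% and effect 30, the expected unadjusted difference is 20 − 30 × 0.20 = 14.0 over all trials. Where the technique enters, it is 13.8 unadjusted and 19.9 adjusted, a rise of 19.9/13.8 − 1 = 44%. Over the six settings the unadjusted difference is 13.8 to 18.4 and the adjusted 19.3 to 19.9. Entry is 19% to 97%.

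**5. A setting with little distortion.** In a separate run of 2,000 trials, use depended on both arm and underlying severity, with a 15-point effect. The mean difference over all trials was 17.3 unadjusted and 17.5 with the technique always adjusted for. The screen was met in only 10.7% of trials. Here the technique's benefit and the severity of those who received it largely offset each other, so distortion is possible but not inevitable.

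**The case against.** **The covariates may be meant as baseline variables.** The same paragraph first uses the covariates to check how well randomization worked, which makes sense only for variables fixed beforehand. Nothing in the plan calls type of anesthesia or co-analgesia a covariate. This reading is plausible, but it does not bind the later screen, which is stated without a limit. Type of anesthesia is extracted yet belongs to none of the four aims, so it is a natural candidate.

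**The adjusted model decides nothing.** This stands. The unadjusted test comes first, and neither the interim boundary nor the final threshold is tied to the adjusted model. The falls in rejection rate above are therefore not a loss of trial power.

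**Under arm-driven use, adjustment recovers the 20 points assumed for dose alone.** True in that simulation, but only because use was made unrelated to pain, and dose alone is a different question from the effect of the assigned strategy.

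**A stronger reading is tempting:** that analgesia will not be identical, that unblinded clinicians will treat the arms differently, and that the primary result is biased or underpowered. The documents do not support this. They describe no arm-driven use and give no rate or direction for it. Same strategies can fairly mean the same menu, and Subject Selection refers to the "ability to utilize medications within our protocol driven multimodal analgesic plan". The Introduction and Significance frame the trial as comparing treatment strategies, and the Randomization Plan aims for generalizability to practice. Under intention to treat, rescue for worse pain belongs to the effect being estimated.

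**Conclusion.** The point holds as a minor gap in the specification of an exploratory model. As written, the screen permits adjustment for type of anesthesia, intraoperative opioids or co-analgesia given after allocation. On assumed inputs, where a rescue technique enters, the adjusted difference is about 14% to 35% below the unadjusted one; under arm-driven use it is higher. Technique effects, triggers and usage rates are all assumptions, so the figures show direction and possible scale, not a forecast. No figure can be derived for opioid consumption. The primary comparison and the stopping rule are untouched. The text between the interim-analysis paragraph and Limitations, and the schema, were not available for this check; if they restrict the covariates, the point falls.

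**What to change.** Add to Biostatistical Analysis: *Covariates eligible for the adjusted models are limited to variables fixed before allocation, for example the anticipated-pain stratum as assigned at randomization, baseline buprenorphine dose, age and sex. Type of anesthesia, intraoperative opioids and co-analgesia given after allocation are not eligible.* Intraoperative opioid use stays available as an Aim 2 measure; it is barred only as a covariate.

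Describe co-analgesic use by arm in one table, from records the plan already keeps.

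The cost is two sentences and a table. No new data item, clinical restriction or change in sample size is needed.
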